Appendix F – Off-Study Form

Study Number: _____ PID: _____

Investigator: [name], DO Date: ____/____/____

Name of Person Competing form _____

Did the subject meet eligibility criteria for study enrollment? Yes No

Was the subject withdrawn from the study? Yes No

Reason(s) for withdrawal:

1. Patient exhibited progression of disease
2. Unacceptable toxicity /adverse event of special interest: if so, list event/submit as adverse event on case report form

If Yes, Please specify whether the toxicity was:

From Bupivacaine
 From Liposomal Bupivacaine
 From BOTH
 Other _____

Adverse event of special interest and reportable to the IRB?

If so, date reported: _____

3. Patient withdraw

If Yes, Please specify what portion of the study the subject wishes to withdraw from:

For just the Drug A administration only
 For just the Drug B administration only
 For both
 For all components of the research study (including follow up in the medical record)

Single Injection interscalene brachial plexus nerve block with adjuvants vs. Liposomal bupivacaine
interscalene brachial plexus nerve block for total shoulder arthroplasty

4. Investigator's discretion to withdraw patient from the study because continued participation in the study is not in the patient's best interest (*Describe below)
5. Undercurrent illness: a condition, injury, or disease unrelated to the intended disease for which the study is investigating, that renders continuing the treatment unsafe or regular follow-up impossible (*Describe below)
6. General or specific changes in the patient's condition that renders the patient ineligible for further investigational treatment (*Describe below)
7. Non-compliance with investigational treatment, protocol-required evaluations or follow-up visits (*Describe below)
8. Termination of the clinical trial by the principal investigator

Comment:

If reason for withdrawal includes #4, 5, 6, or 7 then please add comments clarifying this information) _____

Single Injection interscalene brachial plexus nerve block with adjuvants vs. Liposomal bupivacaine
interscalene brachial plexus nerve block for total shoulder arthroplasty

Appendix G- Pain Medication Diary.

Assists patients in recording the amount and time of narcotic and benzodiazepine use.

| | Date | Pain Medication Used (Include dose) | Number of pills taken | Time |
|----|------|----------------------------------------|-----------------------|------|
| 1 | | | | |
| 2 | | | | |
| 3 | | | | |
| 4 | | | | |
| 5 | | | | |
| 6 | | | | |
| 7 | | | | |
| 8 | | | | |
| 9 | | | | |
| 10 | | | | |
| 11 | | | | |
| 12 | | | | |
| 13 | | | | |
| 14 | | | | |
| 15 | | | | |
| 16 | | | | |
| 17 | | | | |
| 18 | | | | |
| 19 | | | | |
| 20 | | | | |
| 21 | | | | |
| 22 | | | | |
| 23 | | | | |
| 24 | | | | |
| 25 | | | | |
| 26 | | | | |
| 27 | | | | |

Single Injection interscalene brachial plexus nerve block with adjuvants vs. Liposomal bupivacaine interscalene brachial plexus nerve block for total shoulder arthroplasty

| | | | | |
|----|--|--|--|--|
| 28 | | | | |
| 29 | | | | |
| 30 | | | | |
| 31 | | | | |
| 32 | | | | |
| 33 | | | | |
| | | | | |

Appendix H- Data Collection Form

| | |
|--------------|-----------------------------------------|
| | Assigned Study Number: |
| | WakeOne MRN |
| Demographics | Age |
| | Sex |
| Procedure | Comorbidities |
| | Pre-surgical analgesics |
| Medical Hx | Preop pain score |
| | Pre-op multimodal analgesics |
| | Post-Block assessment |
| Pre-Op | Intra-op Narcotics (PO oxy equivalents) |
| | Pain score in PACU p/t discharge |
| Intraop | PACU block assessment |
| | PACU opioids (PO oxy equivalents) |
| | +6hr worst pain score (VAS) |
| PACU | |
| | |

Single Injection interscalene brachial plexus nerve block with adjuvants vs. Liposomal bupivacaine interscalene brachial plexus nerve block for total shoulder arthroplasty

| | |
|------------------|-----------------------------------------------------------------------------------------------------------------------------------------------------------------------------------------------------------------------------------------------------------------------------------------------------------------------------------------------------------------------------------------------------------------------------------------------------------------------------------------------------------------|
| | 
+12h worst pain score (VAS)
 
+24h worst pain score (VAS)
 
+36h worst pain score (VAS)
 
+48h worst pain score (VAS)
 
+6hr opioid use (PO oxy eq)
 
+12h opioid use (PO oxy eq)
 
+24h opioid use (PO oxy eq)
 
+36h opioid use (PO oxy eq)
 
+48h opioid use (PO oxy eq)
 
Likert Satisfaction #1
 
Likert satisfaction #2 Nonopiod Analgesics Used Side effect evaluation (Itching, Nausea/vomiting)
 |
| Post OP | |
| Off study | 
("OFF" if applicable)
 
Reasons:
 |

Date of study completion:

Evaluable subject?

Protocol deviations?

Single Injection interscalene brachial plexus nerve block with adjuvants vs. Liposomal bupivacaine interscalene brachial plexus nerve block for total shoulder arthroplasty

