4.0 Study Outcomes and Study Measures

4.1 Primary Outcome

- 4.1.1 The primary outcome of this study is the area-under-the-curve (AUC) of the mean visual analog scores numerical rating system (VAS-NRS) within the first 48 hours postoperatively. Pain levels (with shoulder movement) will be measured upon arrival to the PACU, at 6 hours, 12 hours, 24 hours, 36 hours, and 48 hours after surgery.
 - 4.1.1.1 The mean AUC48 of the liposomal bupivacaine ISB group was 136.4 with a standard error of 12.09.¹⁰
 - 4.1.1.2 There are no existing data to predict the mean AUC48 for ISB using plain bupivacaine +adjuvants, but we predict that this value will be within 20% of the mean AUC48 of the liposomal bupivacaine group, for a value of ~163.0.

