5.1 Study-Related Activities

Patients will be recruited from 2 sites- Wake Forest Baptist Health (Main Campus) and WFBH Davie. Patient involvement in the study will be initiated upon scheduling of their surgery with the Anesthesiology team. Eligible subjects will be identified via eligibility checklist (Appendix A) and contacted via phone call to inform them of the study and give them a brief overview. On the day of surgery, the consent for the study will be obtained after a pre-operative assessment and prior to initiating the regional block by the RAAPM team.

Single Injection interscalene brachial plexus nerve block with adjuvants vs. Liposomal bupivacaine interscalene brachial plexus nerve block for total shoulder arthroplasty

[figure not shown]
The study coordinator will then assign the patients will receive a study number, and the patient will be randomized by computer software algorithm to one of the study arms:

1. ISB using liposomal bupivacaine
2. ISB using plain bupivacaine with adjuvants

The study will be double blinded to patients, the perioperative nurses, the surgeon, and the study coordinators contacting the patient post-surgery.

To monitor our primary outcomes, patients will be asked to rate their pain level on a visual analog scale (Table 2, Appendix D) upon discharge from the PACU. Following discharge, they will continue to get every 12-hour pain assessments performed by research staff in person and/or over the phone (if they are discharged) until 48 hours have passed.

Table 2: Visual Analog Scale

Additionally, upon discharge, patients will be given a sheet to record the amount of narcotics and the time that they were used (Appendix G). At the 48-hour mark, patient's will be asked to rate their satisfaction with the procedure, and their willingness to recommend it, via Likert scale (Appendix E).

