Appendix C – Pain Assessment Form

Subject Number: _____ DATE: ____/____/____ TIME: ____:____ AM/PM

1 - Rate the intensity of your worst pain in the past 12 hours related to your operated shoulder

0 1 2 3 4 5 6 7 8 9 10

2 - Did you take prescription pain pills in the past 24 hours? YES NO

If yes please circle the medication below

2a1 – Oxycodone (Roxicodone)

2a2 - Hydromorphone (Dilaudid)

2a3 - Hydrocodone + acetaminophen (Vicodin, Norco)

[figure not shown]
2a4- Oxycodone + acetaminophen (Percocet)

2a5 -Diazepam (Valium)

2a6- Alprazolam (Xanax)

Single Injection interscalene brachial plexus nerve block with adjuvants vs. Liposomal bupivacaine interscalene brachial plexus nerve block for total shoulder arthroplasty

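### The data form has no field for the primary outcome as defined: section 4.1.1 calls for pain with shoulder movement, Appendix H records worst pain, and the sections disagree on the PACU moment and the 6 h score

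*Combined protocol and SAP*

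**What the plan says.** **Outcome definition.** Section 4.1.1 makes the primary outcome the AUC of the 0-10 pain score over 48 hours and states how it is measured: "Pain levels (with shoulder movement) will be measured upon arrival to the PACU, at 6 hours, 12 hours", then 24, 36 and 48 hours. Section 5.4 lists the same times.

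**Data form.** Appendix H has one PACU entry, "Pain score in PACU p/t discharge". The later entries run from "6hr worst pain score (VAS" through 12, 24 and 36 h to "48h worst pain score (VAS". All five say worst pain, none gives a recall window, and none mentions movement.

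**Patient question.** Appendix C asks the patient to "Rate the intensity of your worst pain in the past 12 hours related to your operated shoulder". No section of the protocol body cites this form.

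**Procedures and analysis.** Section 5.1 has patients "rate their pain level on a visual analog scale (Table 2, Appendix D) upon discharge from the PACU", after which "they will continue to get every 12-hour pain assessments performed by research staff". Section 6.1.1 likewise speaks of departure from the PACU and 12-hour intervals. Neither mentions 6 h. Table 1 uses PACU departure but has a pain score at 6 h.

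**48 h secondary outcome.** Section 2.2.1 asks for pain control at one time point, 48 hours, and 4.2.1 uses the mean score at that time. The only 48 h pain field in Appendix H is the worst-pain one.

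**The concern.** Pain on movement at a set hour is a provoked, momentary reading. Worst pain is ordinarily the highest level over some stretch of time; it may have occurred at another hour, and at rest. A reading of the first kind can be placed at a clock time on an AUC curve or reported as the 48 h value. A reading of the second kind cannot, unless its window is defined and the summary is built for window maxima.

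If staff complete Appendix H as labelled, the trial will hold a series that is not the one 4.1.1 defines, and the defined one cannot be collected later, because a movement score at 6 or 24 h is lost once the hour has passed. The analysis section does not settle the matter, since it says only that pain scores are used. The choice between versions would then fall to whoever analyses the data, possibly after seeing it.

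The timing conflict is a smaller matter of the same kind. The first point of the curve is at PACU arrival in some sections and at discharge or departure in others, and the role of the 6 h score in the AUC is left open.

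**Working it through.** **1. Sections side by side**

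| Place | Score | PACU moment | 6 h score | Later times |
|---|---|---|---|---|
| 4.1.1 | with shoulder movement | arrival | yes | 12, 24, 36, 48 h |
| 5.4 | not stated | arrival | yes | 12, 24, 36, 48 h |
| Table 1 | not stated | departure | yes | 12, 24, 36, 48 h |
| 5.1 | pain level on Table 2 / Appendix D scale | discharge | not named | every 12 h to 48 h |
| 6.1.1 | pain scores | departure | not named | each 12 h |
| Appendix H | worst pain (PACU entry: pain score) | discharge | yes | 12, 24, 36, 48 h |
| Appendix C | worst pain, past 12 h | none | none | none |

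Only 4.1.1 mentions movement in the visible text. If Appendix C were used at the 6 h contact, its 12-hour window would start 6 hours before the end of surgery, and the 12 h report would overlap the 6 h one.

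**2. The plan's own threshold.** Section 6.1.1: 2 points x 48 h = 96 point-hours. This reproduces.

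**3. Weight of the affected times.** Under the trapezoid rule each score is weighted by half the interval on either side of it. For 0, 6, 12, 24, 36 and 48 h the weights are 3, 6, 9, 12, 12 and 6 hours, which sum to 48. The five scores labelled worst pain carry 6 + 9 + 12 + 12 + 6 = 45 of the 48 hours.

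**4. Size of a mismatch.** Let g be the between-arm difference in the gap (worst pain minus movement pain), taken as constant over the five times. The AUC contrast then shifts by 45 x g. The documents give no value for g, so the range below is an assumption; the sign may be either way.

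| g (points) | Shift (point-hours) | Share of 96 |
|---|---|---|
| 0 | 0 | 0% |
| 0.25 | 11.25 | 11.7% |
| 0.5 | 22.5 | 23.4% |
| 1 | 45 | 46.9% |

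**5. Does the AUC method matter?** Section 6.1.1 names least squares without naming a curve. Fitting the six times and integrating from 0 to 48 h, a straight line gives the five scores a weight of 41.77 and a quadratic 46.36. At g = 0.5 the shifts are 20.9 and 23.2, against 22.5 by trapezoid. The size hardly depends on the method.

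**6. Timing.** Without 6 h the trapezoid weights are 6, 12, 12, 12 and 6, so leaving it out changes one AUC by 3 x (PACU score) + 3 x (12 h score) - 6 x (6 h score). Illustrative profiles at PACU, 6, 12, 24, 36 and 48 h:

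- 0, 0, 2, 4, 4, 3.4: 134.4 with 6 h, 140.4 without (+6)
- 4, 0, 2, 4, 4, 3.4: 146.4 and 164.4 (+18)
- 0, 4, 4, 4, 4, 3.4: 176.4 and 164.4 (-12)

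These are changes in one AUC, not in the contrast between arms. One point of difference between an arrival and a discharge score is worth 3 point-hours with six times and 6 with five.

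**The case against.** The best defence has four parts.

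- **The comparison is protected.** The trial is randomised, patients and the coordinators who call them are blinded, and both arms use the same form. If worst pain exceeds movement pain by the same amount in both arms, the contrast is unaffected. This stands. A reader might infer that the primary comparison is biased; the documents do not support that, because they give no gap in either arm and no evidence that it differs.
- **The instrument cannot be seen.** Section 5.1 ties the primary outcome to Table 2 and Appendix D, whose images are not in the text available. They may carry a movement instruction. This also stands, but it does not change the Appendix H labels, which are legible and say worst pain.
- **Appendix C may serve another purpose.** True: no body section cites it, and its window does not suit a 6 h field. A reader might infer that the AUC will be built from 12-hour maxima. That is one possible reading only, as Appendix H states no window. The mismatch with 4.1.1 rests on Appendix H alone.
- **The 6 h score will probably be collected.** It is in 4.1.1, 5.4, Table 1 and Appendix H, and the 12-hour wording may be loose summary. A reader might infer that 6.1.1 prescribes a five-time AUC; it does not exclude 6 h, so the fair statement is that its use is unclear.

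It is also tempting to judge the shifts against a planned difference of 163.0 - 136.4 = 26.6 point-hours. Section 4.1.1 says "we predict that this value will be within 20% of the mean AUC48 of the liposomal bupivacaine group", and 6.1.1 treats 163.0 as a ceiling. So 26.6 is the upper limit of the prediction, not the expected case, and is not used here as a yardstick.

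**Conclusion.** The point holds as an internal contradiction about what the primary outcome is. The data form, followed as labelled, holds neither the movement-pain series of 4.1.1 nor a single-time-point score for the 48 h secondary outcome. That conclusion rests on visible text and needs no numerical assumption.

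Its effect on the result is unknown. It is zero for the between-arm contrast if the gap between scores is equal in both arms. Otherwise it is 11.25 point-hours per 0.25 point of between-arm difference, about 12% of the 96 point-hour threshold, in either direction. That figure assumes a constant gap at the five later times and trapezoid weights. Even with equal gaps, the trial would report an outcome other than the one it defined. The PACU moment and the 6 h score are minor by comparison but should be settled in the same edit.

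**What to change.** Before data collection:

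1. Keep 4.1.1 and relabel the five Appendix H fields as current pain with shoulder movement, 0-10, at 6, 12, 24, 36 and 48 h.
2. Choose one PACU moment and use it in 4.1.1, 5.1, 5.4, 6.1.1, Table 1 and Appendix H. Section 5.4 changes only if arrival is not kept.
3. Name the 6 h score in 5.1 and 6.1.1, so that its place in the AUC is explicit.
4. State that the 48 h secondary score in 2.2.1 and 4.2.1 is the same item.
5. Align the Appendix C question with 4.1.1, or state that it is not the source of the primary outcome.

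If worst pain was intended, redefine 4.1.1 and 2.2.1 instead, with stated windows that do not overlap and a summary suited to window maxima.

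The cost is five relabelled fields, the PACU field if arrival is kept, one Appendix C item or a sentence about it, and short text edits. If worst pain is wanted as well, it needs a separate field.

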APPENDIX I: ADVERSE EVENT GRADING SCALES

| LOCAL REACTION TO INJECTABLE PRODUCT | Mild (Grade 1) | Moderate (Grade 2) | Severe (Grade 3) | Potential life threatening (Grade 4) |
|--------------------------------------|----------------------------------------------------------|----------------------------------------------------------------------------------|--------------------------------------------------------------|--------------------------------------------------------|
| Pain | Does not interfere with activity | Repeated use of non-narcotic pain reliever >24 hours or interferes with activity | Any use of narcotic pain reliever or prevents daily activity | Emergency room visit or hospitalization |
| Tenderness | Mild discomfort to touch | Discomfort with movement | Significant discomfort at rest | Emergency room visit or hospitalization |
| Erythema/Redness | 2.5-5 cm | 5.1-10 cm | >10 cm | Necrosis or exfoliative dermatitis |
| Induration/Swelling | 2.5-5 cm and does not interfere with activity | 5.1-10 cm or interferes with activity | >10 cm or prevents daily activity | necrosis |
| <hr/> | | | | |
| VITAL SIGNS | Mild (Grade 1) | Moderate (Grade 2) | Severe (Grade 3) | Potentially Life threatening (Grade 4) |
| Fever-*F | 100.4-101.1 | 101.2-102.0 | 102.1-104 | >104 |
| Tachycardia | 101-115 | 116-130 | >130 | ER visit or hospitalization for arrhythmia |
| Bradycardia | 50-54 | 45-49 | <45 | ER visit or hospitalization for arrhythmia |
| Hypertension-systolic | 141-150 | 151-155 | >155 | ER visit or hospitalization for malignant hypertension |
| Hypertension-diastolic | 91-95 | 96-100 | >100 | ER visit or hospitalization for malignant hypertension |
| Hypotension | 85-89 | 80-84 | <80 | ER visit or hospitalization for hypotensive shock |
| Respiratory rate | 17-20 | 21-25 | >25 | Intubation |
| <hr/> | | | | |
| SYSTEMIC (GENERAL) | Mild (Grade 1) | Moderate (Grade 2) | Severe (Grade 3) | Potentially Life threatening (Grade 4) |
| Nausea/vomiting | No interference with activity or 1 – 2 episodes/24 hours | Some interference with activity or > 2 episodes/24 hours | Prevents daily activity, requires outpatient IV hydration | ER visit or hospitalization for hypotensive shock |
| Diarrhea | 2 – 3 loose stools | 4 – 5 stools | 6 or more watery stools or requires IV hydration | ER visit or hospitalization |

Single Injection interscalene brachial plexus nerve block with adjuvants vs. Liposomal bupivacaine
interscalene brachial plexus nerve block for total shoulder arthroplasty

| | | | | |
|------------------------------------------------------------------------------------|-------------------------------|-----------------------------------------------------------------------------------------|---------------------------------------------------------------------------|-----------------------------|
| Headache | No interference with activity | Repeated use of nonnarcotic pain reliever > 24 hours or some interference with activity | Significant; any use of narcotic pain reliever or prevents daily activity | ER visit or hospitalization |
| Fatigue | No interference with activity | Some interference with activity | Significant; prevents daily activity | ER visit or hospitalization |
| Myalgia | No interference with activity | Some interference with activity | Significant; prevents daily activity | ER visit or hospitalization |
| Illness or clinical adverse event (as defined according to applicable regulations) | No interference with activity | Some interference with activity not requiring medical intervention | Prevents daily activity and requires medical intervention | ER visit or hospitalization |
